4.9. Randomisation procedure

Eligible participants who consent will be allocated a unique study ID and randomly assigned to one of the trial arms using a computer-generated blocked stratified (by country) randomisation sequence created using Stata version 15 (or later), with an allocation ratio of 1:1. A statistician based at the University of York, who is not involved in the recruitment of trial participants, will generate the randomisation sequence and online randomization will be done at each trial site to randomly allocate participants to the trial arms, after a participant has provided written informed consent and completed a baseline assessment. Allocation will be recorded on the participant record.

4.11. Blinding

Outcomes will be assessed by researchers blinded to allocation. The trial manager will set up a log of the participants recruited and the RAs who recruited that participant and the RAs who will do the follow-up assessments. It will be strictly ensured that the RAs who will recruit, randomise and allocate a participant to the trial will only complete the baseline assessment for that patient. They will not complete the 3 months and 6 months follow-up CRFs of the study participants which will be undertaken by another RA at the same site.

4.12. Study outcomes

The study will focus on the following primary (feasibility and acceptability) and secondary outcomes: *4.12.1. Primary Outcomes (feasibility and acceptability of recruitment and retention)*

4.12.1.1. Recruitment rates, assessed as the number of participants eligible, consenting and randomised, out of those screened.

4.12.1.2. Reasons for ineligibility/non-participation/non-consent of participants.

4.12.1.3. Length of time required to achieve the required sample size.

4.12.1.4. Retention in the study, assessed as the number of participants randomised who are successfully followed up at 3 and 6 months.

4.12.2. Primary outcomes (feasibility of intervention delivery)

4.12.2.1. Retention in treatment reported as the number of sessions attended out of the total number of sessions offered.

4.12.2.2. Intervention fidelity of delivery of the behavioural activation intervention.

4.12.3. Secondary outcomes (feasibility of baseline and outcomes data collection)

4.12.3.1.Data completeness at baseline and at follow-up

4.13. Baseline and follow-up data collection

We will collect proposed baseline and follow-up measures to test feasibility and burden (time, resources, missing data).

At the baseline, in addition to demographics and socioeconomic status, we plan to record weight, height, Body Mass Index (BMI), waist circumference, hip circumference, waist—hip ratio, smoking status, blood pressure, comorbidities, depression caseness and severity (44), anxiety (48), diabetes distress (49,50), selfefficacy (51,52), diabetes self-management activities (53,54), physical activity (55) diabetes microvascular and macrovascular complications, medication and health-related quality of life (56). We will also investigate blood tests (glycosylated haemoglobin (HbA1_c), haemoglobin level (Hb) and white blood cell count (WBC), renal function tests including serum urea, serum creatinine and estimated Glomerular Filtration Rate (eGFR), lipid function test including triglycerides, total cholesterol, high-Density Lipoprotein cholesterol (HDL), low-Density Lipoprotein cholesterol (LDL), Thyroid function tests including serum triiodothyronine (T3), Thyroxine test (T4), Thyroid-stimulating hormone (TSH), Random blood sugar (RBS), and Liver function test including only serum Alanine Transaminase (ALT).

Following randomisation and baseline data collection, participants in each arm will be followed up at three months. Only severity of depression, anxiety, health-related quality of life and HbA1c will be assessed.

At six months post-randomisation, reassessment of depression caseness and severity, anxiety, selfefficacy, diabetes self-management activities (53,54), physical activity (55), diabetes microvascular and macrovascular complications, medication, health-related quality of life (56), and glycosylated haemoglobin (HbA1_c) will be recorded. Potential mediators (derived from the intervention logic model): Knowledge about depression/symptoms and regarding the link between behaviour and depression, intention to plan and regularly do healthy activities, beliefs about consequences; will also be collected.

Data will be measured and collected from participants and carers face-to-face (or remotely in case of Covid-19 restrictions) at baseline, three and six months as displayed in table 1. The baseline and followup Case Report Form's (CRF) data and anthropometric measurements will be entered directly into an online survey tool (Qualtrics) using tablets at each site. However, for the blood test reports the data will be first entered into a paper format or blood reports log since the reports will include identifiable information (name, age and gender of the participant). From the log, the RAs will shift the information to the qualtrics data sheet mentioning only the study ID and the results.

4.13.1. Demographic data

The demographic profile of recruited participants will be assessed only at the baseline and will be adapted from the WHO STEPwise approach to Surveillance (STEPs) instrument, Version 3.2(57) to collect information about participants' age, sex, education and marital status. STEPs is a standardized tool that

facilitates comparisons within the country or across countries and has already been translated, used and validated in the general population in Bangladesh (58) and Pakistan(59).

4.13.2. Caseness and severity of depression

PHQ-9 (44) will be used to measure depressive symptoms and their severity at baseline, 3 months and 6 months follow-up. This nine-item questionnaire is scored from 0 to 27, and a higher score indicates more severe depressive symptoms.

4.13.4. Anxiety

The generalized anxiety disorder 7 item scale (GAD-7)(48,60) will be administered at baseline, 3 months and 6 months follow-up, to measure the severity of generalised anxiety disorder. It comprises seven questions and each question has been assigned the score of 0, 1, 2, and 3, concordant with the respective responses of 'not at all', 'several days', 'more than half the days', and 'nearly every day'. The total sum of the scores represents the final score (maximum attainable score is 21) with the cut off points of 5 for mild anxiety, 10 for moderate and 15 for severe anxiety.

4.13.5. Diabetes-related distress

The tool, Problem Areas in Diabetes Scale-5 (PAID-5), will be administered that consist of 5 items that measure Diabetes-related emotional distress with a focus on various common problems and feelings associated with living with diabetes(50). It determines the effect on the patients, on a scale of 0 (not a problem) to 4 (serious problem). The scores when summed up and standardized indicate levels of diabetes-related distress whereby scores \geq 8 indicate diabetes-related distress.

4.13.6. Diabetes-related self-efficacy and self-management

An eight-item version of the Diabetes Empowerment Scale-Short form (DES-SF)(51) will be used to measure overall diabetes-related psychosocial self-efficacy. However, for the assessment of self-care, the Perceived Diabetes Self Management Scale (PDSMS)(52) will be administered. PDSMS comprises 8 items for which the responses may range from 1 (Strongly Disagree) to 5(Strongly Agree) where 4 items are reverse scored. The total PDSMS score may range from 8 to a maximum attainable score of 40, where higher scores indicate higher confidence in self-management.

Diabetes-related self-management activities will also be specifically determined through the Summary of self-care diabetes activities scale (SDSCA) that includes 11 items that determine different diabetes self-management activities pertinent to general diet, specific diet, exercise, blood-glucose testing, foot care and smoking (53).

4.13.7. Diabetes-related microvascular and macrovascular complications

The complications of diabetes will be assessed based on the self-reporting (i.e. history based on being informed by a health care provider) of the participants at baseline as well as 6-month follow-up. For confirmation of any previous episode or existent macrovascular complications (coronary artery disease, peripheral arterial disease, and stroke) as well as microvascular complications (diabetic nephropathy, neuropathy and retinopathy) of diabetes, related questions will be inquired as part of CRF, at baseline and at 6-month follow-up.

4.13.8. Physical activity

The International Physical Activity Questionnaires (IPAQ) short version (9 items), will be applied to determine the physical activity of the participants at baseline(55). The tool acquires information related to activities at four intensity levels for the last 7 days, i.e. 1) vigorous-intensity activity such as aerobics, 2) moderate-intensity activity e.g. leisure cycling, 3) walking, and 4) sitting.

4.13.9. Quality of life

Euroqol's instrument EQ-5D-5L will be administered to measure health-related quality of life (HRQoL). EQ-5D is a standardized measure of health status developed by the EuroQol Group. It provides a simple, generic measure of health for clinical and economic appraisal, where health is characterised on five dimensions; mobility, self-care, ability to undertake usual activities, pain/discomfort, anxiety/ depression(61). Patients' subjective evaluation of their health state based on a visual analogue scale (EQ-5D-VAS) is also included in the scale, ranging from "0 (representing worst imaginable health state) to the maximum attainable value of 100 (indicating best imaginable health state).

4.13.11. Physical body measurements

Physical body measurements will be measured by RAs, according to the WHO STEPS surveillance manual(57), at baseline and at 6-month follow-up, including the following:

1. Weight

The weight of the participant will be measured, in the unit "kilograms" using a portable digital weighing scale placed on a firm flat surface. Two consecutive readings to two decimal places will be recorded into CRF. Participants will be advised to get the weight recorded by mounting on a scale with light clothing and without footwear and socks.

2. Height

A portable height measuring board without footwear and headgear will be used to measure the height of the participants, in the unit "centimetres". Duplicate readings, to a precision of 0.1 cm will be recorded into the CRFs.

3. Body Mass Index

Body Mass Index (BMI) measurement is reflective of the nutritional status in adults. It is defined as a person's weight in kilograms divided by the square of the person's height in metres (kg/m2). The RAs will enter the height and weight in the BMI calculator in their tablets that will be computed for the participants that will be recorded in the CRFs.

4. Waist circumferences:

Waist circumference will be measured, using a flexible anthropometric tape, in the unit "centimetres". It will be measured at the midpoint between the lower margin of the last palpable rib and the top of the iliac crest (hip bone), with the arms relaxed at the sides when the participant will exhale fully at the end of expiration. Two consecutive readings will be taken to a precision of 0.1 cm.

5. Hip circumference:

Hip circumference will be measured, using a flexible anthropometric tape, in the unit "centimetres". It will be measured by wrapping the tape around the widest portion of the buttocks, with the tape parallel to the floor. Two consecutive readings will be taken to a precision of 0.1 cm.

6. Waist-hip ratio: The waist-hip ratio is an indicator or measure of health, the risk of developing serious health conditions and obesity. The waist-hip ratio is calculated as waist measurement divided by hip measurement. The RAs will enter the height and weight in the hip-waist ratio calculator in their tablets that will be computed for the participants that will be recorded in the CRFs.

7. Blood pressure

Blood pressure (BP) and Heart/pulse rate will be measured using an automated blood pressure measuring instrument (OMRON[®]). Three consecutive readings (each with 3 minutes gap) from the same wrist/elbow will be taken using the same device and recorded in CRFs. Before taking the measurements, the

participant must be comfortable and seated. The study participant will be informed about the readings only after the whole process is completed. The measurements will be taken from the left wrist/arm but in case there will be a stroke of that side/limb then it will be measured from the right side

4.13.12. Tobacco & alcohol Use

Health risk behaviour questions adapted from the STEPs tobacco and smokeless tobacco modules (core module and a few questions from expanded module)(57) will be used to identify current tobacco users of smoked or used smokeless tobacco in the past 30 days. Moreover, questions related to alcohol use will also be used to assess the alcohol consumption status over the last 12 months.

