	 h. Blood tests: Haemoglobin level (Hb), white blood cell count (WBC), renal function tests including serum urea, serum creatinine and estimated Glomerular Filtration Rate (eGFR), lipid function test including triglycerides, total cholesterol, high-density lipoprotein cholesterol (HDL), low-density lipoprotein cholesterol (LDL), thyroid function tests including serum triiodothyronine (T3), thyroxine test (T4), thyroid-stimulating hormone (TSH), random blood sugar (RBS), and liver function test only serum Alanine Transaminase (ALT); (baseline only) i. Weight, height, BMI, waist circumference, hip circumference, waist-hip ratio, and blood pressure. j. Potential mediators (derived from the intervention logic model): Knowledge about depression/symptoms and regarding the link between behaviour and depression, intention to plan and regularly do healthy activities, beliefs about consequences. k. Changes in avoidance and activation over the course of Behavioral Activation for depression.(PAAS)
	 Health care resource use, out-of-pocket payments, cost of delivering the DiaDeM intervention, economic outcomes, employment status, productivity loss and the

	opportunity cost of time. and other economic data including patient self-report using an adapted Client Service Receipt Inventory and health service data.
Number of participants	128 in total, 64 in intervention and 64 control arm
Main inclusion/ exclusion criteria	 Inclusion Criteria: Adults (≥18 years old) diagnosed with type 2 diabetes, confirmed by the health care staff of the diabetes centres based on their standardized diagnostic criteria that include HbA1_c, clinical presentation and diabetes centre's registration record. Persons scoring ≥3 on Patient Health Questionnaire-2 (PHQ-2) that will be administered by the health care staff at Diabetes centre as part of depression screening and mild, moderate or severe depression confirmed if scoring ≥5 on Patient Health Questionnaire-9 (PHQ-9) and through Mini-International Neuropsychiatric Interview (MINI). Willing to participate Able to attend therapy sessions in person or remotely. Exclusion Criteria: Already receiving psychotherapy for depression. Lacking capacity to provide informed consent. Unable to take part in therapy because of cognitive impairment, or severity of mental or physical illness.
Estimated period of recruitment	3 months
Total duration of follow-up per participant	6 months
Blinding	Outcomes will be assessed by researchers blinded to allocation

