Health risk behaviour: Tobacco use	An adapted version of The STEPs tobacco and smokeless tobacco modules.	х		х
Health risk behaviour: Alcohol use	Adapted questions of the STEPs alcohol module.	Х		х
Diabetes complications	A set of questions in DiaDeM CRF on Diabetes-related microvascular and macrovascular complications.	х		х
Health-related quality of life (HRQoL)	EQ5D-5L including visual analogue scale (EQ-5d-VAS)	Х	х	х
Mediators	A set of questions in DiaDeM-CRF for potential mediators including; Knowledge about depression/symptoms and regarding the link between behaviour and depression, intention to plan and regularly do healthy activities, beliefs about consequences, derived from the intervention logic model	X	X	Х

OUTCOMES	Scales	Baseline	Month 3	Month 6
Changes in avoidance and activation over the course of Behavioral Activation for depression	PREMIUM Abbreviated Activation Scale (PAAS)	х	х	х
Economic outcomes: 1. Employment Status 2. Household status 3. Productivity Loss (income and days (hours) of work lost) 4. Out-Of-Pocket Payments (OOP) 5. Opportunity Cost of Time (average wage and time) 6. Borrowing / Selling Assets 7. Household earnings and Expenditure 8. Catastrophic Health Spending (OOP as % of household expenditure)	Set of questions related to economics outcomes in DiaDeM CRF adapted from Asset index questionnaire	X		X
Health care resource use	Modified client service receipt Inventory (CSRI)	х		х
Medication	Modified client service receipt Inventory (CSRI)	х		х

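### The month-6 alcohol question looks back 12 months, so it masks stopping or cutting down after randomisation; the open-ended complications question cannot show a repeat episode

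*Protocol*

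**What the plan says.** **Alcohol.** Section 4.13.12 gives the only recall window stated for this measure: "questions related to alcohol use will also be used to assess the alcohol consumption status over the last 12 months". The alcohol row of Table 1, described as "Adapted questions of the STEPs alcohol module", is marked at baseline and month 6. The prose list of month-6 measures in section 4.13 does not name alcohol, so the repeat rests on Table 1.

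**Complications.** Section 4.13.7 relies on self-report. The purpose is worded "For confirmation of any previous episode or existent macrovascular complications", with microvascular complications treated in the same way, and "related questions will be inquired as part of CRF, at baseline and at 6-month follow-up". No wording limits the month-6 question to the time since baseline.

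**Follow-up.** The Summary states "Total duration of follow-up per participant 6 months".

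**Other windows.** The tobacco questions in 4.13.12 identify "current tobacco users of smoked or used smokeless tobacco in the past 30 days". The physical activity questionnaire covers 7 days (4.13.8) and the resource-use questionnaire six months (section 6).

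**Use of the data.** Section 4.13 collects the measures to test feasibility and burden. Section 4.12.3 makes data completeness the secondary outcome. Section 4.15 summarises clinical outcome measures descriptively by arm and by severity.

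**The concern.** A follow-up measure should describe the period after randomisation, or at least be separable from what came before. A single 12-month answer given at month 6 mixes 6 months before with 6 months after, and no analysis can split it afterwards. A complications question that covers all past history has a similar limit in participants who already answered yes at baseline.

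Two things are at stake. The month-6 summaries by arm would partly describe behaviour from before allocation. And because the stated test of these measures is completeness, an item with an unsuitable window could be fully completed, look feasible, and be proposed for the full trial without the problem being noticed.

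**Working it through.** The protocol states no figure to reproduce on this point. The check is window arithmetic, followed by an illustration that rests on an assumption.

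**Inputs**
- Alcohol recall L = 12 months (4.13.12).
- Month-6 visit at F = 6 months after randomisation (4.13 and Summary).
- Alcohol measured at baseline and month 6 (Table 1).

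**Step 1: the windows.** With randomisation at time 0, the baseline answer covers months −12 to 0 and the month-6 answer covers months −6 to +6.
- Months before randomisation in the month-6 window: L − F = 12 − 6 = 6.
- Share of the window: 6/12 = 50%.
- These 6 months are already in the baseline window.

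**Step 2: which changes can be seen on a user/non-user item**
- Non-user at baseline who starts during follow-up: no, then yes. Visible.
- Drank between months −6 and 0, stopped at randomisation: yes, then yes. Masked.
- Drank only between months −12 and −6, none since: yes, then no. This looks like stopping during follow-up, although drinking ended before randomisation.

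**Step 3: illustration of masking.** Assume a drinker has a chance q of drinking in any month, months are independent, and every drinker stops at randomisation. The protocol gives no value for q. The share of baseline users still classed as users at month 6 is

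[1 − (1−q)^6] / [1 − (1−q)^12]

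| q | numerator | denominator | still positive |
|---|---|---|---|
| 0.05 | 0.265 | 0.460 | 58% |
| 0.1 | 0.469 | 0.718 | 65% |
| 0.2 | 0.738 | 0.931 | 79% |
| 0.5 | 0.984 | 1.000 | 98% |

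The ratio simplifies to 1 / [1 + (1−q)^6], so under these assumptions it is above 50% for every q above 0.

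**Step 4: illustration of dilution.** If the CRF also asks an average amount over the same 12 months, a steady drinker who stops at randomisation reports 6/12 = 50% of the baseline amount at month 6, although current intake is nil.

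**Step 5: shorter windows.** With 6 months, 6 − 6 = 0 months fall before randomisation. With 30 days, none do either.

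**Step 6: complications, item by item**
- No, then no: no event reported.
- No, then yes: first-ever complication, identified by linking to baseline.
- Yes, then yes: cannot separate a repeat episode from old history.

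**The case against.** **New events can be seen.** A reader might infer that these items cannot show change at all. They can: both are taken at baseline, so new drinking and first-ever complications are visible. The loss is confined to stopping or cutting down, and to repeat episodes.

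**Adverse-event reporting is a second channel.** A reader might also infer that repeat complications are lost to the trial. Section 10.1 lists angina, myocardial infarction, stroke and amputation among potential adverse events, section 10.3 has events assessed at every contact in both arms, and section 10.4 places serious complications under standard reporting. A repeat stroke or coronary event can therefore be recorded there. That leaves the less serious complications that 10.4 makes non-reportable (retinopathy, neuropathy and the milder diabetic foot), and the questionnaire item itself.

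**Nothing decisive depends on these items.** They are neither primary outcomes nor progression criteria, and no analysis of change is stated. This stands and limits the importance. It does not remove the point, because section 4.15 still summarises clinical measures by arm.

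**The CRF is not shown.** It may contain shorter-window questions or follow-up wording. That is fair, but 12 months is the only alcohol window the protocol states.

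**Other items share the form.** Comorbidities (4.13.14) are also recorded as any diagnosed history and repeated at month 6, so complications are not unique in this. Among the health-risk behaviours, however, alcohol is the only one whose stated window exceeds the follow-up.

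**Conclusion.** The point holds as a minor measurement fault. Half of the month-6 alcohol window (6 of 12 months) precedes randomisation, so stopping is masked in anyone who drank in the 6 months before baseline, and cutting down is diluted. Under the assumptions shown, 58% to 98% of baseline users would still be classed as users after complete cessation, for monthly drinking chances of 0.05 to 0.5; this range is illustrative. The 50% overlap depends only on the stated window and visit time. For complications, the questionnaire identifies first-ever events but not repeats in someone already positive.

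The conclusion assumes that the month-6 CRF follows the protocol's description. The documents do not support saying that a result of this trial would be wrong, or that the same wording will necessarily pass into the full trial: section 2.3.3 makes testing the proposed tools one of the trial's own questions. The practical value of a correction lies in the month-6 summaries by arm and in the choice of measures for the full trial.

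**What to change.** - **Alcohol:** at month 6, use a recall window no longer than the follow-up, and add an item with the same window at baseline so that the two visits compare. Six months captures any use since randomisation, but still classes as a user someone who stopped part-way through follow-up. Thirty days, as for tobacco, captures current use but misses drinking earlier in follow-up. Either removes the overlap. The existing 12-month item can stay at baseline.
- **Complications:** keep the history question at baseline. At month 6, ask about new or repeat episodes since the baseline visit.
- **Protocol text:** state the windows in 4.13.7, 4.13.12 and Table 1. If the CRF already words the questions this way, a clarifying sentence in each of these places is enough.

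The cost is CRF wording in the online survey tool and one extra baseline item, with no added visit or procedure.
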